## **5. ENDPOINTS**

### **5.1 PRIMARY ENDPOINTS**

Primary PK endpoints are as defined in Section 2.1.2 of the CTP.

Primary endpoints in Part 1 are  $AUC_{0-\infty}$  for (C-14) BI 1358894 i.v. and  $AUC_{0-\infty}$  for BI 1358894 p.o.

Primary endpoint of Part 2 is  $AUC_{0-312}$  of BI 1358894.

### **5.2 SECONDARY ENDPOINTS**

#### **5.2.1 Key secondary endpoint**

Not applicable

#### **5.2.2 Secondary endpoints**

Secondary PK endpoints will be as defined in Section 2.1.3 of the CTP.

Secondary endpoint in Part 1 is  $C_{max}$  of BI 1358894.

Secondary endpoints in Part 2 are  $C_{max}$  and  $AUC_{0-\infty}$  of BI 1358894.

Further safety parameters of interest will be as defined in **Section 2.2.2.2 of the CTP**:

- AEs (including clinically relevant findings from the physical examination)

## **5.4 OTHER VARIABLES**

### **5.4.1 Demographic and other baseline characteristics**

**Section 5.2.1 of the CTP:** *At screening, the medical examination will include demographics, height and body weight, smoking and alcohol history (results not mandatory to be entered into CRF or to be reported), relevant medical history and concomitant therapy, review of inclusion and exclusion criteria, review of vital signs (BP, PR), 12-lead ECG, laboratory tests, a physical examination and a neurological examination.*

Body mass index will be calculated as weight (kg) / [height (m)].

#### **5.4.2 Treatment compliance and treatment exposure**

Treatment compliance will not be analysed as a specific endpoint, cf. Section 4.3 of the CTP.

Treatment exposure is defined as the number of doses and the total dose of BI 1358894 per treatment and per subject.

## 6. GENERAL ANALYSIS DEFINITIONS

### 6.1 TREATMENTS

For basic study information on treatments to be administered, assignment of treatment groups, and selection of doses, cf. Section 4 of the CTP.

The trial is divided into two parts, with the same patients included in both parts.

In **Part 1**, each subject is planned to be treated with a single oral dose (two non-radiolabelled tablets) of BI 1358894 (T1) on Day 1. Five hours after the administration of the tablet, the subjects will receive an i.v. microtracer dose of [C-14]-BI 1358894 (R1).

In **Part 2**, each subject is planned to be treated with a single oral suspension of BI 1358894 either under fasted (R2) or fed (T2) conditions on Day 1 in each period separated by a washout period of at least 17 days between the two drug administrations. The subjects will be randomly allocated to the two treatment sequences T2-R2 or R2-T2.

Single oral drug administrations of each period are separated by a washout period of at least 17 days.

Table 6.1: 1 Flow chart of analysis phases for statistical analyses of AEs

Analysis phase	Label	Start (inclusive)	End (exclusive)
Screening	Screening	Date of informed consent	Date/time of first administration of BI 1358894 in Part 1
On-treatment	BI Tab	Date/time of first administration of BI 1358894 tablet in Part 1	Date/time of start of infusion of BI 1358894 (C-14) in Part 1
On-treatment	BI Tab/C14	Date/time of start of infusion of BI 1358894 (C-14) in Part 1	Date/time of end of infusion of BI 1358894 (C-14) in Part 1 + REP (11*24h)
Follow-up	F/U BI	Date/time of end of infusion of BI 1358894 (C-14) in Part 1 + REP (11*24h)	Date/time of first administration of BI 1358894 in Part 2
On-treatment	BI fasted	Date/time of administration of BI 1358894 under fasted conditions in Part 2	Date/time of administration of BI 1358894 under fasted conditions in Part 2 + REP (11*24h)
Follow-up	F/U BI fasted	Date/time of administration of BI 1358894 under fasted conditions in Part 2 + REP (11*24h)	Date/time of administration of BI 1358894 under fed conditions in Part 2 or 12:00 a.m. on day after subject's trial termination date, whichever occurs earlier
On-treatment	BI fed	Date/time of administration of BI 1358894 under fed conditions in Part 2	Date/time of administration of BI 1358894 under fed conditions in Part 2 + REP (11*24h)
Follow-up	F/U BI fed	Date/time of administration of BI 1358894 under fed conditions in Part 2 + REP (11*24h)	Date/time of administration of BI 1358894 under fasted conditions in Part 2 or 12:00 a.m. on day after subject's trial termination date, whichever occurs earlier

Analysis phases for statistical analysis of AEs are defined for each subject as described in the [Table 6.1: 1](#).

CTR Section 15, Appendix 16.1.13.1.8.2 and Appendix 16.1.13.1.8.3 AE displays will present results for the on-treatment phases only.

In CTR Section 15 AE tables (but not in Appendix 16.1.13.1.8.2 and Appendix 16.1.13.1.8.3 AE tables), the following totals will be provided in addition:

- "**Total BI**", defined as the total over all on-treatment phases involving BI

In disposition, demographics and baseline characteristics, all subjects will be analysed together (i.e., one "Total" column).

Safety laboratory data, vital signs and ECG will be analysed by treatment (BI, BI fasted, BI fed) with clear differentiation between baseline (cf. [Section 6.7](#)) and on-treatment measurements. Measurements will be considered on-treatment, if they were taken within the on-treatment phases as defined in Table 6.1: 1.

The following labels will be used for the comparison of treatments:

Table 6.1: 2 Overview of treatments for intra-individual comparison

Treatment	Short label
R1 100 µg BI 1358894 (C-14)	BI (C-14) 100 ug iv
T1 100 mg BI 1358894	BI 100 mg tablet
R2 100 mg BI 1358894 under fasted conditions	BI 100 mg fasted
T2 100 mg BI 1358894 under fed conditions	BI 100 mg fed

More details on the technical implementation of these analyses are provided in the ADS Plan of this TSAP.

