7.3.4 Safety analyses

Safety will be analysed based on the assessments described in Section [2.2.2.2](#). All treated subjects (TS, refer to Section [7.2](#)) will be included in the safety analysis. Safety analyses will be descriptive in nature and based on BI standards. No hypothesis testing is planned.

For all analyses, the treatment actually administered (= treatment at onset) to the subject will be used (any deviations from the randomised treatment will be discussed in the minutes of the Report Planning Meeting).

Treatments will be compared in a descriptive way. Tabulations of frequencies/proportions will be used to evaluate categorical (qualitative) data, and tabulations of descriptive statistics will be used to analyse continuous (quantitative) data.

Measurements (such as ECG, vital signs, or laboratory parameters) or AEs will be assigned to treatments (see Section [4.1](#)) based on the actual treatment at the planned time of the measurement or on the recorded time of AE onset (concept of treatment emergent AEs). Therefore, measurements planned or AEs recorded prior to first intake of trial medication will be assigned to the screening period, those between first trial medication intake (test

Proprietary confidential information © 2020 Boehringer Ingelheim International GmbH or one or more of its affiliated companies

treatment) and beginning of reference treatment will be assigned to the test treatment period. Those between the start of infusion until the end of REP (see Section [1.2.2](#)) will be assigned to the combined test/reference treatment period. Events occurring after the REP but prior to next intake or end of trial termination date will be assigned to 'follow-up'. These assignments including the corresponding time intervals will be defined in detail in the TSAP. Note that AEs occurring after the last per protocol contact but entered before final database lock will be reported to Pharmacovigilance only and will not be captured in the trial database.

Additionally, further treatment intervals (analysing treatments) may be defined in the TSAP in order to provide summary statistics for time intervals, such as combined treatments, on-treatment totals, or periods without treatment effects (such as screening and follow-up intervals).

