7.6 RANDOMISATION

Part 1:

Randomization is not applicable in this open-label and single group clinical study part. All subjects will receive the same treatment. Consecutive subject numbers will be assigned via the EDC system.

Part 2:

Subjects will be randomised to one of the 2 treatment sequences in a 1:1 ratio. The block size will be documented in the CTR.

The sponsor will arrange for the randomisation as well as packaging and labelling of trial medication. The randomisation list will be generated using a validated system that uses a pseudo-random number generator and a supplied seed number so that the resulting allocation is both reproducible and non-predictable.

The randomisation list will contain additional blocks to allow for subject replacement (refer to Section [3.3.5](#)).

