## 7. PLANNED ANALYSIS

The format of the listings and tables will follow the BI guideline "Standards for Reporting of clinical trials and project summaries" ([6](#)).

The individual values of all subjects will be listed. Listings will be sorted by treatment sequence ("Tab/C14-fasted-fed" and "Tab/C14-fed-fasted"), subject number and visit (if visit is applicable in the respective listing). AE listings will be sorted by assigned treatment (see [Section 7.8.1](#) below for details). The listings will be contained in Appendix 16.2 (SDL) of the CTR.

The following standard descriptive statistical parameters will be displayed in summary tables of continuous variables:

N	number of non-missing observations
Mean	arithmetic mean
SD	standard deviation
Min	minimum
Median	median
Max	maximum

For plasma concentrations as well as for all PK parameters the following descriptive statistics will additionally be calculated:

CV	arithmetic coefficient of variation
gMean	geometric mean
gCV	geometric coefficient of variation

For PK parameters the following descriptive statistics will additionally be calculated:

P10	10 th percentile
Q1	1 st quartile
Q3	3 rd quartile
P90	90 th percentile

The data format for descriptive statistics of plasma concentrations will be identical with the data format of the respective concentrations. The descriptive statistics of PK parameters will be calculated using the individual values with the number of decimal places as provided by the evaluation program. Then the individual values as well as the descriptive statistics will be reported with three significant digits in the CTR.

Tabulations of frequencies for categorical data will include all possible categories and will display the number of observations in a category as well as the percentage (%) relative to the respective treatment group. Percentages will be rounded to one decimal place. The category missing will be displayed if and only if there actually are missing values. Percentages will be based on all subjects in the respective subject set whether they have non-missing values or not.

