### 7.8.1 Adverse Events

AEs will be coded with the most recent version of MedDRA.

The analyses of AEs will be descriptive in nature. All analyses of AEs will be based on the number of subjects with AEs and not on the number of AEs.

For further details on summarization of AE data, please refer to "Analysis and Presentation of Adverse Event Data from Clinical Trials" ([7](#)) and "Handling of missing and incomplete AE dates" ([3](#)).

The analysis of AEs will be based on the concept of treatment emergent AEs. That means that all AEs will be assigned to screening, on-treatment or follow-up phases as defined in [Section 6.1](#). AEs will be analysed based on actual treatments, as defined in [Table 6.1: 1](#).

An overall summary of AEs will be presented. This overall summary will comprise summary statistics for the class of AESIs.

**CTP Section 5.2.6.1.4:** *The following are considered as AESIs:*

- Hepatic injury  
*A hepatic injury is defined by the following alterations of hepatic laboratory parameters:*
  - *An elevation of AST (aspartate transaminase) and/or ALT (alanine transaminase)  $\geq 3$ -fold ULN combined with an elevation of total bilirubin  $\geq 2$ -fold ULN measured in the same blood sample, or*
  - *Aminotransferase (ALT, and/or AST) elevations  $\geq 10$  fold ULN*

The investigator had to classify on the eCRF whether an observed AE was an AESI or not.

According to ICH E3 ([8](#)), in addition to deaths and SAEs, "other significant" AEs need to be listed in the clinical trial report. These will be any non-serious adverse event that led to an action taken with study drug (e.g. discontinuation or dose reduced or interrupted).

An overall summary of adverse events will be presented.

The frequency of subjects with AEs will be summarised by treatment, primary SOC and preferred term. AEs which were considered by the investigator to be drug related will be

summarised separately. Separate tables will also be provided for subjects with SAEs and subjects with AESIs. AEs will also be summarized by maximum intensity.

The SOCs and preferred terms within SOCs will be sorted by descending frequency over all treatment groups.

For disclosure of AE data on ClinicalTrials.gov, the frequency of subjects with non-serious AEs occurring with an incidence of greater than 5 % (in preferred terms) will be summarised by treatment, primary SOC and preferred term. The frequency of subjects with SAEs will also be summarised.

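### Does the last Part 2 follow-up phase in SAP Table 6.1: 1 end before it starts, leaving late adverse events without a phase?

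*SAP*

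**What the plan says.** SAP Section 6.1 says that the analysis phases for adverse events are defined for each subject by Table 6.1: 1. Both Part 2 follow-up phases start at the subject's own dose plus the residual effect period of 11*24 h. Their ends are:

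- F/U BI fasted: "Date/time of administration of BI 1358894 under fed conditions in Part 2 or 12:00 a.m. on day after" the trial termination date, whichever occurs earlier.
- F/U BI fed: "Date/time of administration of BI 1358894 under fasted conditions in Part 2 or 12:00 a.m. on day after" the trial termination date, whichever occurs earlier.
- F/U BI (after Part 1): "Date/time of first administration of BI 1358894 in Part 2", with no termination alternative.

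Both orders of the food conditions occur. SAP Section 6.1 states "The subjects will be randomly allocated to the two treatment sequences T2-R2 or R2-T2", and protocol Section 7.6 states "Subjects will be randomised to one of the 2 treatment sequences in a 1:1 ratio".

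Two other places bear on the meaning. Protocol Section 7.3.4 gives the parent rule: "Events occurring after the REP but prior to next intake or end of trial termination date will be assigned to" follow-up, with the detailed intervals left to the SAP. SAP Section 7.8.1 says that "all AEs will be assigned to screening, on-treatment or follow-up phases".

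**The concern.** The rows are labelled by food condition, not by period, and each uses the other condition's dose as its end without saying that this dose must be the later one. In T2-R2 the fed dose comes first, so the end of F/U BI fasted lies before its start. In R2-T2 the same happens to F/U BI fed. The termination alternative does not help, because the earlier of the two dates is always the dose already given.

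If programmed that way, the follow-up phase after the final dose would be empty for every subject dosed in both Part 2 periods. That could be all 12 planned subjects, about 6 per sequence. The stretch concerned includes the last 312 h visit and the end-of-trial examination, at both of which adverse events are asked for. Such an event would be neither on-treatment nor in follow-up, against both the protocol rule and SAP Section 7.8.1. Its position in the listings would also be unclear, since "AE listings will be sorted by assigned treatment".

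**Working it through.** **Inputs**

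- Residual effect period: 11 days (protocol Section 1.2.2) and 11*24 h (SAP Table 6.1: 1). Check: 11 × 24 = 264 h, so the two agree.
- Gap between doses: at least 17 days = 17 × 24 = 408 h (SAP Section 6.1).
- End-of-trial examination: Day 52 to 57 (protocol Flow Chart Part 2 and Appendix 10.2).
- Assumptions: Day 52 to 57 is counted from the Part 1 tablet, time 0 is that tablet at 08:00, and all gaps are exactly 17 days unless stated.

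**Dates.** Doses fall at 0, 408 and 816 h. Midnight after Day 52 is 51 × 24 + 16 = 1240 h; midnight after Day 57 is 56 × 24 + 16 = 1360 h.

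**Formulas**

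- Start = own dose + 264 h.
- Literal end = min(other condition's dose, midnight after termination).
- Protocol end = min(next dose if any, midnight after termination).

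**Sequence R2-T2, termination on Day 52**

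| Phase | Start (h) | Literal end (h) | Literal length (h) | Protocol end (h) | Protocol length (h) |
|---|---|---|---|---|---|
| F/U BI fasted | 408 + 264 = 672 | 816 | +144 | 816 | +144 |
| F/U BI fed | 816 + 264 = 1080 | 408 | −672 | 1240 | +160 |

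T2-R2 gives the same figures with the labels exchanged. In general the literal length of the last follow-up phase is −(gap + 264 h). It is therefore negative at every permitted gap; at 18 days it is −(432 + 264) = −696 h. The first Part 2 follow-up phase is the same under both rules. A subject with only one Part 2 dose is not affected, because the other date is missing and the phase closes at termination.

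**Size of the stretch without a phase.** With 17-day gaps it is 1240 − 1080 = 160 h to 1360 − 1080 = 280 h. With 18-day gaps the last dose is at 864 h and its on-treatment phase ends at 864 + 264 = 1128 h, giving 112 to 232 h. The 312 h visit lies 312 − 264 = 48 h into it.

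**Which outputs use the end of a follow-up phase**

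- Adverse event displays in report Section 15 and the two appendices named in SAP Section 6.1: on-treatment phases only.
- The total over BI: a sum over on-treatment phases.
- Baselines (SAP Section 6.7): a value is barred only if it lies in an on-treatment phase.
- Laboratory, vital signs and ECG: on-treatment status follows the on-treatment rows.
- Pharmacokinetic endpoints: no phase is used.
- Individual listings (SAP Section 7): all subjects' values are listed, so a late event still appears; only its sort label depends on the phase.
- Concomitant therapy: SAP Section 7.2 refers to the analysis phase of a treatment without saying whether follow-up belongs to it. Protocol Section 7.3.4 presents therapies without regard to time intervals.

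**The case for a change.** The strongest argument for a change is that the protocol hands the detailed intervals to the SAP, so this table is the controlling definition, and it drops the idea of the next intake. The stretch contains planned adverse event questioning, the table fails once for each subject dosed in both Part 2 periods, and a repair would cost a few words. The arithmetic behind this stands in full.

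It does not follow that an analyst would be misled. A phase that ends 28 days (672 / 24) before it begins cannot be programmed as an interval, so the reader must look for the intended rule, and the documents supply it. SAP Sections 3 and 4 say that the SAP elaborates protocol Section 7 and accords with it, and the protocol says next intake. SAP Section 7.8.1 requires a phase for every event, and one starting after the final residual effect period can only be in follow-up. The table points the same way: the termination alternative appears only in the two Part 2 follow-up rows, one of which is the last phase of each subject who completes. On the literal reading, that alternative would never operate for anyone dosed in both periods.

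The missing termination bound in F/U BI adds nothing, since for a subject never dosed in Part 2 that phase stays open and no event drops out. The therapy point rests on reading follow-up into SAP Section 7.2, which the text does not establish. SAP Section 6.1 also leaves the technical implementation to the ADS Plan. That plan is not among the documents, so neither correct nor faulty programming can be shown.

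**Conclusion.** No change follows. The two Part 2 follow-up end cells are loosely worded: taken literally, the last follow-up phase has length −(gap + 264 h), or −672 h at the minimum gap, in both sequences. This is a drafting slip that analysts will resolve in the only workable way, by counting the other dose only when it comes later.

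The last phase then runs from 264 h after the final dose to trial termination: 160 to 280 h with 17-day gaps, if Day 52 to 57 is counted from the Part 1 dose and dosing is at 08:00. The clock times in the flow charts are approximate, so these hours are indicative.

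Nothing in the named adverse event displays, the BI total, the baselines or the pharmacokinetic estimates depends on the choice. What remains is the phase label of any late event in datasets and listings, and such events are listed in any case. The conclusion assumes that the programming follows the protocol's next-intake rule.

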## 6.2        IMPORTANT PROTOCOL DEVIATIONS

Consistency check listings (for identification of deviations from time windows) and a list of protocol deviations (e.g. deviations in drug administration, in blood sampling times, etc.) will be provided to be discussed at the Report Planning Meeting (RPM). At this meeting, it will be decided whether a discrepant data value can be used in the analyses or whether it must be corrected in the clinical database. Each protocol deviation must be assessed to determine whether it is an important protocol deviation (iPD). For definition of iPDs, and for the process of identification of these, refer to the BI reference document "Identify and Manage Important Protocol Deviations (iPD)" (2). Additionally, all iPDs will be documented in the DV sheet.

If any iPDs are identified, they are to be summarised into categories and will be captured in the decision log. Categories which are considered to be iPDs in this trial are defined in the integrated quality and risk management plan (IQRMP). If the data show other iPDs, the definition in the IQRMP and the table below will be supplemented accordingly by the time of the RPM.

iPDs will be summarized and listed. Table 6.2: 1 below specifies which kind of iPDs could potentially lead to exclusion from which analysis set (cf. [Section 6.3](#)). The decision on exclusion of subjects from analysis sets will be made at the latest at the RPM, after discussion of exceptional cases and implications for analyses.

Non-important COVID-19 related PDs will only be listed.

Table 6.2: 1 Handling of iPDs

iPD code	iPD Category & Brief Description	Excluded from which analysis set
A1	Inclusion Criteria Not Met	PKS
A2	Exclusion Criteria Violated	PKS
B1	Informed consent not available/not done	TS, PKS
B2	Informed consent too late	None
C1	Incorrect trial medication intake	PKS
C2	Randomisation not followed	PKS
C3	Non-compliance	PKS
C4	Medication code broken inappropriately	PKS
C5	Incorrect intake of trial medication	PKS
C6	Improper washout between treatments	PKS
D1	Prohibited medication use	PKS
D2	Mandatory medication not taken	PKS
D3	Improper washout of prohibited concomitant medication	PKS
E1	Certain violations of procedures used to measure primary or secondary data	PKS
F1	Certain violations of time schedule used to measure primary or secondary data such as incorrect duration of infusion	PKS
G1	Incorrect intake of meal	PKS

### 6.3 SUBJECT SETS ANALYSED

Subject sets will be used as defined in the **Section 7.3 of the CTP**:

- *Treated set (TS): The treated set includes all subjects who were randomized and treated with at least one dose of study drug. The treated set will be used for safety analyses.*
- *Pharmacokinetic parameter analysis set (PKS): This set includes all subjects in the treated set (TS) who provide at least one PK endpoint that was defined as primary or*

*secondary and was not excluded due to a protocol violation relevant to the evaluation of PK or due to PK non-evaluability (as specified in the following subsection 'Pharmacokinetics'). Thus, a subject will be included in the PKS, even if he contributes only one PK parameter value for one period to the statistical assessment. Descriptive and model based analyses of PK parameters will be based on the PKS.*

In addition, the following subject set for a certain analysis of ECG data will be used.

All ECG analyses are performed on the TS, except for the exposure-response analyses, which are performed on the ECGPCS defined below.

- ECG plasma concentration set (ECGPCS):  
This subject set includes all subjects from the TS who provide at least one pair of a valid drug plasma concentration and a corresponding (i.e. time-matched) ECG endpoint to be used in the exposure-response analyses. The decision whether a time deviation between PK blood sampling and ECG recording is acceptable (and thus whether the pair of values will be used) is to be made no later than at the RPM before data base lock.

Table 6.3: 1 Subject sets analysed

Class of endpoint	Subject set		
	TS	PKS	ECGPCS
Disposition	X		
IPDs	X		
Primary endpoints		X	
Secondary endpoints		X	
Further PK endpoints		X	
Safety parameters (except for exposure-response analyses of ECG data)	X		
Exposure-response analyses of ECG data			X
Demographic/baseline conditions	X		
Exposure	X		

